1.32 Rationale for regorafenib pharmacokinetic studies

Regorafenib has clinical activity in CRC, but many patients discontinue treatment in the first 2 cycles due to adverse events (Grothey A et al. 2013). In the few phase I studies to date, small patient numbers underwent any PK evaluation at steady state beyond cycle 1, to understand a possible connection between toxicity and PK parameters.

Because this clinical trial seeks to optimize the regorafenib dose and overall exposure in patients with refractory mCRC, it is critical that we evaluate the pharmacokinetic parameters of regorafenib and its metabolites, and assess whether their PK variability is clinically relevant. To our knowledge, no large pharmacokinetic correlative studies – or those studies evaluating if plasma regorafenib concentrations are associated with its efficacy or toxicity – have been conducted to date.

Therefore, as detailed in Section 14.1, we have developed a clinic-friendly sampling schedule to collect the PK trough levels (C_{\min}) for the study drug and its metabolites, to maximize patient compliance. In the low dose (dose escalation) cohort, as the regorafenib dose is planned to be escalated weekly in cycle 1 from 80 to 120 to 160mg, trough levels will be collected on days 7, 14 and 21, when each regorafenib dose would be expected to reach steady state. These visits coincide with regular clinic visits for safety/toxicity evaluation. In cycle 2, PK will be collected on days 1 and 21. To be able to compare the low dose, escalating cohort with the standard dose cohort, similar time-points for PK analysis were chosen.

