2.3 Correlative Research

- 2.31 Evaluate and compare trough (C_{\min}) PK during the first 2 treatment cycles for regorafenib and active metabolites M2, M5 between the low dose (dose escalation) and the standard dose cohorts, and correlate with toxicity profile.
- 2.32 Evaluate the correlation between PK parameters and tumor response/stable disease after the first two cycles.
- 2.33 Evaluate the correlation between PK parameters and PFS and OS.
- 2.34 Evaluate if trough (C_{\min}) concentrations are associated with patient-specific factors (such as – but not limited to – age and concomitant medications).

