4.0 Test Schedule

Tests and procedures	Active Monitoring Phase										
	≤7 days prior to randomization	Cycle 1 ¹³				Cycle 2 ¹³				After week 8: Every 4 weeks until progression (+/- 3 days)	At PD, withdrawal or removal
		Week 1 (Day 1)	Week 2 (Day 8)	Week 3 (Day 15)	Week 4 (Day 22)	Week 1 (Day 1)	Week 2 (Day 8)	Week 3 (Day 15)	Week 4 (Day 22)		
History and exam, weight, ECOG PS ¹² , blood pressure	X	X ¹²	X	X	X	X	X	X	X	X	X
Height	X										
Adverse event assessment ⁸	X		X	X	X	X	X	X	X	X	X
Hematology ^{8, 11} : CBC/ differential, ANC, INR/PTT ^{8, 10}	X	X				X				X	
Chemistry ^{8, 11} : SGOT (AST), alk phos, T. bili, serum creatinine, calcium, glucose, Na, K, SGPT (ALT)	X	X		X ⁷		X ⁷		X ⁷		X	
Albumin	X										
Urine proteinuria or urine protein creatinine ratio	X										
Tumor measurement ⁸ (CT scan of chest, abdomen and pelvis) (MRI if CT is not feasible)	X ¹								X ¹	X ¹	X ^{1,9}
ECG ⁶	X										
Serum pregnancy test	X ²										
Mandatory blood sample (see Section 14.0)	X ^{4,R}	(Day 7) X ^{4,R}	(Day 14) X ^{4,R}	(Day 21) X ^{4,R}		(Day 1) X ^{4,R}		(Day 21) X ^{4,R}			
Patient Medication Diary (Appendix II) ³		X	X	X	X	X	X	X	X	X	
Patient Questionnaire Booklets (Appendices IV, V, VI)	X ⁵		X ^{5,8}			X ^{5,8}	X ^{5,8}		X ^{5,8}		

1. CT scans preferred (MRI if CT is not feasible) of the chest, abdomen and pelvis. Use same imaging throughout the study. Tumor measurements at baseline (≤28 days prior to randomization) and every 8 weeks until progression.
2. For women of childbearing potential only.

3. The diary must begin the day the patient starts taking the medication and must be completed per protocol and returned to the treating institution weekly during Cycles 1 and 2 and every 4 weeks thereafter.
 4. Kits are required for this collection. Samples will be collected for PK analysis of C_{min} of regorafenib, M2 and M5 at the following time points: Cycle 1, days 7, 14 and 21 prior to treatment; Cycle 2, days 1 and 21, prior to treatment. Samples will be collected for research banking at the following time points: Baseline, prior to treatment; Cycle 2, days 1 and 21, prior to treatment. See Section 14.0 for specific instructions.

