- 6.22 After the patient has been registered into the study, the patient will be assigned to one of the following treatment groups, in 1:1:1:1 fashion, using the Pocock and Simon dynamic allocation procedure which balances the marginal distributions of the stratification factors between the treatment groups (Pocock-Simon, 1975).
- Arm A 1: Regorafenib Cycle 1: 80 mg daily Week 1/120 mg daily Week 2/160 mg daily week 3 then 1 week off followed by Cycle 2+ (160 mg for 21 days/1 week off) + pre-emptive strategy for PPES starting Cycle 1 Day 1
 - Arm A 2: Regorafenib Cycle 1: 80 mg daily week 1/120 mg daily week 2/160 mg daily week 3 then 1 week off followed by Cycle 2+ (160 mg for 21 days/then 1 week off) + reactive strategy for PPES
 - Arm B 1: Regorafenib 160 mg daily for 21 days/then 1 week off + pre-emptive strategy for PPES starting Cycle 1 Day 1
 - Arm B 2: Regorafenib 160 mg daily for 21 days/then 1 week off + reactive strategy for PPES

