7.11 Arm A Regorafenib Dose Escalation

Cycle 1:

Week	Dose
1 Starting Dose	80 mg*
2	120 mg
3	160 mg
4	Off

*starting dose level

Cycle 2 and beyond:

Week	Dose
1	Remain at highest tolerated dose from Cycle 1 (up to 160 mg)
2	
3	
4	Off

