8.1 Arm A Regorafenib Dose Escalation/Reduction

Dose level	If No SDRT	If + SDRT**
80 mg*	Proceed to next dose level	-
120 mg	Proceed to next dose level	Decrease to 80 mg
160 mg	-	Decrease to 120 mg

*starting dose level

**SDRT = Significant Drug Related Toxicities

- 8.11 After week 8, if toxicities have resolved to \leq Grade 0-1, re-escalation is allowed 40 mg at a time every 4 weeks to a maximum of 160 mg and at the discretion of the treating investigator.
- 8.12 Patients with dose reductions below 80 mg should go off treatment and go to event monitoring.
- 8.13 Any patients with toxicities requiring >4 week delay should go off treatment and then to event monitoring.

Regorafenib may be dose reduced per the table in Section 8.2 in case of intolerable toxicity such as weight loss, fatigue, rash or anorexia.

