14.2 Study Methodology and Storage Information

14.21 Blood/blood product samples will be collected for pharmacokinetic analysis.

PK analysis for regorafenib and M2 and M5 will be performed as follows:

- Cycle 1 day 7: 0, prior to dosing (C_{min} , trough levels)
- Cycle 1 day 14: 0, prior to dosing (C_{min} , trough levels)
- Cycle 1 day 21: 0, prior to dosing (C_{min} , trough levels)
- Cycle 2 day 1: 0, prior to dosing (C_{min} , trough levels)
- Cycle 2 day 21; 0, prior to dosing (C_{min} , trough levels)
- Window sampling times are predose \leq 12 hours.

14.211 A portion of the plasma, 0.5 ml (500 μ l), for each sample will initially be analyzed for the amount of regorafenib in [name] laboratory using standard laboratory protocols. The samples will be shipped upon request to

[REDACTED]

[REDACTED]

According to patient consent information, remaining white blood cells/plasma will be stored frozen at -70/-80°C by BAP until specific analyses are identified. As protocols are developed, they will be presented for ACCRU and IRB review and approval. (This collection is part of a general strategy of investigation for the majority of ACCRU studies.)

- 14.212 Ongoing research is likely to identify putative biomarkers for regorafenib efficacy and/or toxicity in the near future. Given the key importance of such biomarker identification, our study offers a unique opportunity to validate such discoveries given its size and prospective nature. As such, and as part of ongoing ACCRU research, we will collect plasma and white blood cells for future research studies, according to patient consent information, on molecular determinants of efficacy and tolerability. Samples will be stored frozen at -70°C by BAP until specific analyses are identified. As protocols are developed, they will be presented for ACCRU (scientific) and IRB review and approval prior to any samples being used.

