- 16.46 Furthermore, patients will be descriptively compared between treatment arms and between HFS treatment strategies (pre-emptive vs. reactive) according to self-reported outcomes given on the HFS14 questionnaire. See Section 2.24. Results from the cycle 1 and 2 HSF14 questionnaires will also be summarized descriptively as they relate to the pre-emptive versus reactive PPES strategies, with comparisons made within and between arms using the t-test or Wilcoxon rank sum test as appropriate, as well as taking time-dependence into account. Changes in QOL (according to the LASA questionnaire as measured by the overall QOL question) from baseline will also be compared between the treatment arms using the t-test or Wilcoxon rank sum test. We hypothesize that patients receiving regorafenib will experience greater deficits in QOL as reflected by scores on the HSF14, the BFI and the LASA. These questionnaires have specific application to this population. See Section 2.24.
- 16.47 Pharmacokinetic Analysis
- The samples will be analyzed for the regorafenib concentrations using liquid chromatography mass spectrometry, with the anticipated method being a modified version

of that published by Van Erp et al. The samples will be analyzed for M2 and M5, if cost-free standards can be obtained from Bayer.

After quantitation, the average regorafenib concentration will be calculated by arms (Arm A vs. B) at each time point.

As exploratory analysis, this average concentration will be correlated with toxicity and efficacy endpoints. Further descriptive characteristics of the pharmacokinetics will also be calculated. An example includes (but is not limited to) within-patient variability in the trough concentrations pharmacokinetic parameters will also be calculated, both overall and within cycles, as a ratio of the maximum:minimum value.

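### The Cycle 2 Day 1 sample follows the week off drug, so the within-cycle-2 max:min ratio in 16.47 measures washout rather than within-patient trough variability

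*Combined protocol and SAP*

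**What the plan says.** Section 16.47 offers, as one example of further descriptive PK characteristics, within-patient variability in trough concentrations, calculated "both overall and within cycles, as a ratio of the maximum:minimum value".

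The samples that feed it are fixed elsewhere. Footnote 4 to the Test Schedule (section 4.0) states "Samples will be collected for PK analysis of C_{min} of regorafenib, M2 and M5" and names Cycle 1 Days 7, 14 and 21 and Cycle 2 Days 1 and 21. Section 1.32 confirms "In cycle 2, PK will be collected on days 1 and 21". Section 14.21 has the entry "Cycle 2 day 1: 0, prior to dosing" and gives it the same C_min/trough label as the other four.

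In both arms week 4 of each cycle is off drug. Section 6.22 gives the standard arms as "Regorafenib 160 mg daily for 21 days/then 1 week off", and section 7.11 shows week 4 as off for arm A. Nothing in 4.0, 14.21 or 16.47 sets Cycle 2 Day 1 (C2D1) apart from the on-treatment samples.

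**The concern.** A trough is the concentration at the end of a dosing interval during continued dosing, here 24 h. C2D1 comes after a seven-day gap. Because cycle 2 has only two samples, its max:min ratio has to be a steady-state trough divided by a post-break residual. The overall ratio has the same problem if C2D1 is included, since C2D1 will normally supply the minimum.

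Such a ratio depends on the patient's half-life and time off drug, not on how much the trough fluctuates under constant dosing. Followed as written, the plan would report drug elimination over a scheduled break as within-patient variability. Goal 2.31 also asks for trough PK over both cycles to be compared between arms and to "correlate with toxicity profile", so the label could carry C2D1 into those correlations.

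A smaller, related point: the arm A cycle 1 ratio contains the planned 80/120/160 mg steps.

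**Working it through.** **Inputs from the documents.** Regorafenib half-life: 20 to 30 h (section 1.31) and 28 h, range 14 to 58 h (15.15). M5 half-life: 60 h, range 40 to 100 h (1.31) and 51 h, range 32 to 70 h (15.15). Less than dose-proportional PK above 60 mg (1.31). Pre-dose sampling window up to 12 h (14.21).

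**Assumptions.** First-order elimination. For the full-schedule check, a one-compartment model with absorption rate 0.5/h. A within-patient CV, because the documents give none.

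**1. The plan's own figure.** Section 1.31 puts steady state within 7 days of the first dose. The fraction reached after 168 h is 1 − 2^(−168/t½): 99.7% at 20 h, 98.4% at 28 h, 97.9% at 30 h. The statement reproduces. The same kinetics mean that seven days off remove nearly all the drug.

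**2. Timing of C2D1.** The last cycle 1 dose is on Day 21 and C2D1 is Day 29: 8 × 24 = 192 h after the last dose, and 192 − 24 = 168 h later than a normal trough.

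**3. Cycle 2 ratio from washout alone, 2^(168/t½).**

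| Analyte | t½ (h) | Left at C2D1, % of a trough | Ratio |
|---|---|---|---|
| Regorafenib | 14 | 0.02 | 4096 |
| Regorafenib | 20 | 0.3 | 338 |
| Regorafenib | 28 | 1.6 | 64 |
| Regorafenib | 30 | 2.1 | 48.5 |
| Regorafenib | 58 | 13.4 | 7.4 |
| M5 | 51 | 10.2 | 9.8 |
| M5 | 60 | 14.4 | 7.0 |

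Over the quoted M5 ranges (32 to 100 h) the ratio runs from 38 down to 3.2.

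**4. Full planned schedule by superposition, t½ 28 h.**
- Cycle 2 ratio: 64.3 in arm A, 64.0 in arm B.
- Overall ratio with C2D1: the same 64.3 and 64.0.
- Overall ratio without C2D1: 2.06 in A (1.46 if concentration rises as dose to the power 0.5, an assumption) and 1.03 in B.
- Cycle 1 ratio in A: 2.04 (1.45 at exponent 0.5), which is the escalation. In B it is 1.01 to 1.04 at 20 to 30 h and 1.21 at 58 h.
- C2D21/C1D21: in A 1.00 to 1.01 at 14 to 30 h and 1.05 at 58 h (M5: 1.06 at 60 h, 1.13 at 100 h); in B 1.00 to 1.01 throughout. This pair is almost free of schedule effects.

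**5. What true trough variability would give.** For two lognormal troughs with σ = √ln(1 + CV²), the median max:min is exp(0.6745 × √2 × σ): 1.21, 1.32 and 1.57 at CV 20%, 30% and 50%, and 2.21 at CV 100%. Against the 20% to 50% range, the cycle 2 ratio is too large by:
- Regorafenib, 30 to 20 h: 48.5/1.57 = 31 to 338/1.21 = 280 times.
- Regorafenib, 58 h: 7.4/1.57 = 4.7 to 7.4/1.21 = 6.1 times.
- M5 at its means: 7.0/1.57 = 4.4 to 9.8/1.21 = 8.1 times.

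**6. What the ratio responds to.** At 28 h its median stays at about 64 for every CV from 20% to 100%. Now take CV 30% (σ² = 0.0862) and a lognormal half-life with median 28 h and 14 to 58 h as its 95% range (an assumption). The SD of log half-life is ln(58/14)/3.92 = 0.363. The log ratio ln2 × 168/t½ then has variance about 2.77, against 2 × 0.0862 = 0.17 from trough fluctuation. Half-life supplies 2.77/2.94 = 94% of the variance. The correlation with the absolute fluctuation, which is what a max:min ratio should capture, is about 0.

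**7. Delay.** Section 8.13 reads "Any patients with toxicities requiring >4 week delay should go off treatment", so shorter delays of cycle 2 can occur. One extra week off drug gives 2^(336/28) = 4096 instead of 64. If 10% or 20% of patients (assumed) had that delay, half-life and time off drug together would explain 97% or 98% of the variance.

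**The case against.** The strongest reply is that little depends on this. Section 16.47 presents the ratio as an illustration among descriptive characteristics, with no test, arm comparison or decision attached, and goals 2.31 to 2.34 do not name it. The sampling schedule is plain, so a careful analyst could see that C2D1 follows a break. All of that stands and limits the severity, but the rule as written still returns washout.

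Other points, and what is left of them:
- *C_min is defensible.* A pre-dose Day 1 sample is the lowest point of the 28-day cycle. True, but it is then a different quantity from a 24-h trough and cannot share a ratio with one.
- *The correlations may not be affected.* 16.47 computes average concentrations at each time point, and no text explicitly pools C2D1 with on-treatment troughs. This stands: the harm there is conditional on C2D1 being used.
- *The 12-h window.* Drawing C2D1 12 h early gives 2^(156/t½), about 37 to 223 at 30 to 20 h. The conclusion is unchanged.
- *A larger CV.* At 100% the lowest multiple for regorafenib at 30 h falls to 48.5/2.21 = 22. For M5 at 100 h, washout (3.2) is close to ordinary variability (2.21), so the point is much weaker there.
- *Very large ratios may not be observable.* Section 15.15 describes enterohepatic circulation, so a single-exponential decline is an approximation. No quantitation limit is given. If unquantifiable values counted as missing, section 16.8 would exclude them. The plan does not say how they are treated.
- *Correlation with the signed fluctuation is not zero.* It is 0.24, falling to 0.15 with 20% delayed. A max:min ratio ignores sign, so the absolute fluctuation is the relevant comparison.

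**Conclusion.** The concern holds and is minor. Under the planned schedule the within-cycle-2 ratio, and the overall ratio if C2D1 is included, measure elimination over the break. For regorafenib the expected value is about 48 to 338 at mean half-lives of 30 to 20 h, where true troughs would give a median near 1.2 to 1.6. At the longest quoted half-life of 58 h it is still 7.4. For M5, which is assayed only if cost-free standards are obtained, the inflation is smaller.

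The washout figures rest on the protocol's half-lives and first-order decline; the comparison values rest on an assumed within-patient CV. Not affected are the primary endpoint, the arm means at C1D7, C1D14, C1D21 and C2D21, and the arm B cycle 1 ratio for regorafenib at mean half-lives. The harm is confined to this descriptive measure and to any trough correlation under 2.31 to 2.34 that uses C2D1.

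**What to change.** - In 14.21 and 16.47, and for consistency in footnote 4 of section 4.0, label C2D1 a post-break residual sample and report it separately.
- Exclude it from the max:min trough ratio and from trough-exposure correlations.
- Drop the within-cycle-2 ratio, because only one trough (Day 21) remains.
- Compute the ratio across on-treatment steady-state troughs at the same dose actually taken, for example C1D21 and C2D21 when the dose is unchanged.
- Read the result descriptively, not as a randomised comparison of arms.

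The cost is wording only, with the same samples and assays. Some information is given up. There would be no within-cycle-2 ratio, and no same-dose cycle 1 ratio for arm A patients who escalate as planned. The C1D21/C2D21 pair exists only for patients who reach C2D21 on an unchanged dose, a group selected after randomisation by tolerance, which the dosing arms are designed to change. Dose-normalising all on-treatment samples would keep more data, but the less than proportional PK reported in section 1.31 makes that harder to interpret.

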16.5 Adverse Event Stopping Rule

Because this study randomizes patients to either a standard of care treatment or a lower dose of the same treatment, stopping rules for toxicity will not apply. However, as noted below in Section 16.7, regular meetings of the DSMB will review all toxicity and adverse event data while patients are being treated.

16.6 Accrual Monitoring Stopping Rule

There is no stopping rule related to accrual.

16.7 Study Monitoring

This study will be monitored by the Mayo Clinic Data Safety Monitoring Board (DSMB). Reports containing patient characteristics, toxicity and administrative information will be provided to the DSMB every six months, with the first report due at the first reporting period after study initiation.

16.8 Missing Data

Patients with missing data will be excluded from relevant analyses; no imputation of missing data will be performed.

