7.12 Arm B Regorafenib Dose (all cycles)

Week	Dose
1 Starting Dose	160 mg
2	
3	
4	Off

- 7.2 Patients can be instructed in administration techniques and granted treatment independence with nursing staff approval.
- 7.3 For this protocol, the patient must return to the consenting ACCRU institution for evaluation at least every 7 days during treatment and every 28 days during active monitoring.
- 7.4 Treatment by a local medical doctor (LMD) is not allowed.

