13.0 Treatment/Follow-up Decision at Evaluation of Patient

- 13.1 A patient is deemed *ineligible* if after registration, it is determined that at the time of registration, the patient did not satisfy each and every eligibility criteria for study entry. The patient may continue treatment off-protocol at the discretion of the physician as long as there are no safety concerns, and the patient was properly registered. The patient will go directly to the event-monitoring phase of the study (or off study, if applicable).
- If the patient received treatment, all data up until the point of confirmation of ineligibility must be submitted. Event monitoring will be required per Section 18.0 of the protocol.
 - If the patient never received treatment, on-study material must be submitted. Event monitoring will be required per Section 18.0 of the protocol.
- 13.2 A patient is deemed a major violation, if protocol requirements regarding treatment in cycle 1 of the initial therapy are so severely violated that evaluability for the primary endpoint is questionable. All data up until the point of confirmation of a major violation must be submitted. The patient will go directly to the event-monitoring phase of the study. The patient may continue treatment off-protocol at the discretion of the physician as long as there are no safety concerns, and the patient was properly registered. Event monitoring will be required per Section 18.0 of the protocol.
- 13.3 A patient is deemed a cancel if he/she is removed from the study for any reason before any study treatment is given. On-study material and the End of Active Treatment/Cancel Notification Form must be submitted. No further data submission is necessary.
- 13.4 Patients will continue treatment until progression, unacceptable adverse events, or patient refusal. Treatment will then be discontinued and the patient will go to event monitoring and be followed per Section 18.0.
- 13.5 Patients who are CR, PR, or SD will continue treatment per protocol.
- 13.6 Patients who develop PD while receiving therapy will go to the event-monitoring phase.
- 13.7 Patients who go off protocol treatment for reasons other than PD will go to the event-monitoring phase per Section 18.0.

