16.2 Sample Size, Accrual Time and Study Duration

Accrual time is anticipated to be 18 months, with approximately 2 months of follow-up per patient until occurrence of the primary endpoint and approximately 6 months of planned follow-up overall per patient. The sample size will be 110 patients, with approximately 28 patients randomized per regorafenib and strategy treatment sub-arm (A1, A2, B1, B2). An additional 13 patients overall will be enrolled to account for drop-out, cancels, ineligibles, etc., to give a total sample size of 123 patients. The total study duration (accrual and follow-up) is expected to be approximately 2 years.

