16.3 Statement for Primary Endpoint

The primary endpoint is the proportion of patients in each arm who complete 2 cycles of protocol treatment and initiate cycle 3. The proportion will be calculated among evaluable patients separately by arm (Arm A vs. Arm B). Evaluable patients are defined as patients who are eligible, consented, received any protocol treatment. In the CORRECT trial, among patients who were randomized to regorafenib, 45% continued treatment beyond cycle 2. Other than disease progression, majority of patients discontinued regorafenib due to adverse events not associated with progression. It was noted that most adverse events occurred during Cycles 1-2 of the treatment (Grothey A et. al., 2013, Lancet). Assuming 45% of patients would complete 2 cycles of protocol treatment and initiate cycle 3 in the control (standard dose; pooled arms B1 and B2) group, and desiring an improvement to 63% in the experimental (starting low dose) group (pooled arms A1 and A2), a one-sided test with $\alpha = 0.20$ and power of 80% will require a sample size of 110 patients enrolled to both regorafenib arms (A and B). We will enroll 13 additional patients to account for ineligibility, cancellation, major treatment violation, or other reasons. Maximum projected accrual is therefore 123 patients. A Fisher exact test will be used to detect a difference in proportion of patients who complete 2 cycles of protocol treatment and initiate cycle 3 between arms (starting low dose [pooled arm A1 and A2] vs. standard dose [pooled arm B1 and B2]). The proportion of patients who complete 2 cycles of protocol treatment and initiate cycle 3 will be computed by arm with its 95% confidence interval using exact method.

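### Does the missing-data rule in 16.8, read with 13.2, leave the primary denominator open for treated major violations and unknown cycle 3 status?

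*Combined protocol and SAP*

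**What the plan says.** The primary endpoint is set out in section 16.3: "The primary endpoint is the proportion of patients in each arm who complete 2 cycles of protocol treatment and initiate cycle 3". The same section fixes who is counted: "Evaluable patients are defined as patients who are eligible, consented, received any protocol treatment".

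Three other statements bear on that denominator.

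- Section 13.2 defines a major violation as a patient whose cycle 1 treatment requirements were "so severely violated that evaluability for the primary endpoint is questionable". The patient moves to event monitoring and data up to that point are submitted. On later therapy, 13.2 says: "The patient may continue treatment off-protocol at the discretion of the physician as long as there are no safety concerns". It does not say that the patient leaves the primary analysis.
- The allowance of 13 patients is explained in two ways. Section 16.3 has "We will enroll 13 additional patients to account for ineligibility, cancellation, major treatment violation, or other reasons", and section 16.2 has "An additional 13 patients overall will be enrolled to account for drop-out, cancels, ineligibles, etc".
- Section 16.8, on missing data in general, reads "Patients with missing data will be excluded from relevant analyses; no imputation of missing data will be performed".

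On follow-up, section 7.3 states that "the patient must return to the consenting ACCRU institution for evaluation at least every 7 days during treatment". Section 18.1 requires a treatment form at each evaluation, an Off Treatment form at the end of treatment, and a Lost to Follow-Up form where applicable.

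**The concern.** Read together, these passages could support two denominators. One analyst applies the 16.3 definition and keeps every eligible treated patient. Another notes the doubt in 13.2, sees major violations listed in the allowance beside ineligible patients and cancels (both already outside the denominator), takes 16.8 at its word, and removes major violations and patients of unknown status.

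The choice is not neutral for an individual patient. The endpoint counts protocol treatment, so a major violation who continues off-protocol cannot be a success. If kept, the patient is a failure; if removed, the patient vanishes. The decision would come after randomisation, and no blinding is described. Cycle 1 dosing differs between the arms (three planned dose steps in arm A, one dose in arm B), so unequal numbers of violations are conceivable. In a close result one patient can matter: in a hypothetical table, 30/55 against 25/55 gives a one-sided Fisher p of 0.223, while 30/54 against 25/55 gives 0.194, on the other side of 0.20.

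**Working it through.** **Inputs (16.3 and 16.1).** Control rate 0.45, target 0.63, one-sided alpha 0.20, power 80%, Fisher exact test, 1:1 allocation of pooled A to pooled B, 110 patients plus 13.

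**The plan's own figure.** With d = 0.18, mean rate 0.54 and z = 0.8416 for both alpha and power:

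- Uncorrected n per arm = [z√(2 × 0.54 × 0.46) + z√(0.45 × 0.55 + 0.63 × 0.37)]² / d² = [0.8416 × (0.7048 + 0.6933)]² / 0.0324 = 42.7.
- Continuity-corrected n = (42.7/4) × [1 + √(1 + 4/(42.7 × 0.18))]² = 53.3, so 54 per arm, or 108 in total.
- Exact enumeration at 55 per arm: power 0.804, actual type I error 0.146 at 45% in both arms.
- 110/0.90 = 122.2, rounded up to 123.

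The sample size is sound, and this question does not alter it.

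**What the text decides for each group.**

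| Group | Meets the 16.3 definition? | Outcome known? | Result as written |
|---|---|---|---|
| Cancel (untreated, 13.3) | No | – | Out |
| Ineligible (13.1) | No | – | Out |
| Treated, documented stop before cycle 3 | Yes | Yes | Failure |
| Treated major violation, sent to event monitoring | Yes | Yes | Failure |
| Treated, cycle 3 status unknown | Yes | No | Kept by 16.3; 16.8 could be read to drop |

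Only the last row shows a real clash, and frequent visits and the 18.1 forms should make it nearly empty.

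**Size if failures were removed.** P(reject) = Σ over x, y of Bin(x; 55, pA) × Bin(y; 55, pB) × 1[Fisher p ≤ 0.20], with kA and kB failures removed before the test. The k values are assumptions; the documents give none.

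| Removed (A, B), 55 per arm | Type I error | Power |
|---|---|---|
| 0, 0 | 0.146 | 0.804 |
| 2, 2 | 0.146 | 0.804 |
| 4, 4 | 0.146 | 0.807 |
| 3, 1 | 0.194 | 0.859 |
| 4, 2 | 0.195 | 0.863 |
| 2, 0 | 0.194 | 0.856 |
| 3, 0 | 0.233 | 0.893 |
| 4, 0 | 0.253 | 0.908 |
| 0, 2 | 0.108 | 0.747 |
| 0, 4 | 0.083 | 0.682 |

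With 61 per arm (nobody lost from the 123, an upper bound) the base type I error is 0.158. Removing 2 or 3 from arm A only gives 0.206 or 0.210, and the (3, 1) and (4, 2) splits both give 0.206.

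**Size if violations are kept as failures but have nothing to do with tolerability** (k patients forced to failure, the rest binomial, 55 per arm).

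| Forced failures (A, B) | Type I error | Power |
|---|---|---|
| 2, 0 | 0.108 | 0.732 |
| 4, 0 | 0.077 | 0.647 |
| 0, 3 | 0.210 | 0.871 |
| 0, 4 | 0.235 | 0.890 |
| 2, 2 | 0.141 | 0.789 |
| 4, 4 | 0.137 | 0.772 |

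Excluding such patients independently of outcome, 2 or 4 from one arm, gives type I error 0.142 to 0.151 and power 0.795 to 0.801.

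**Equal shares at 61 per arm.** If an assumed 5% of each arm is affected, power is 0.825 with exclusion and 0.818 with failures kept. At 10% it is 0.804 and 0.790.

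**The case for a change.** The best argument for a change is that 16.3 does not sit easily with itself. It defines a denominator that contains treated major violations, then enrols extra patients to make up for them, as if they would be lost. Section 13.2 adds that their evaluability is in doubt and gives no criteria for the label. Section 16.8 does not exempt the primary endpoint. Nothing states which passage prevails, and with no blinding described, a late decision to remove one non-completer could tip a borderline result.

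Part of this stands. The reasons given for the allowance are not matched to the definition, and the precedence of 16.3 over 16.8 is left to the reader. But an allowance only says how many patients to enrol; it does not create an analysis set. The doubt expressed in 13.2 leads to event monitoring, not to an instruction to exclude. Section 16.8 does not reach the main group, because a major violation who has left protocol treatment has a known outcome. A rule for relevant analyses most naturally fits questionnaires and blood samples, which do go missing. The ordinary reading, that the definition specific to the primary endpoint governs it, gives one answer.

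**Conclusion.** The concern does not call for a change. Followed as written, 16.3 keeps treated major violations and counts them as not having started cycle 3, which is a sound analysis. What is left is missing detail: loosely worded reasons for the 13 extra patients, and no sentence ranking 16.3 above 16.8. An analyst would sensibly count a treated patient with no recorded start of cycle 3, under visits at least every 7 days, as a non-completer.

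The size depends on assumptions. Equal removal leaves type I error at 0.146 with 55 per arm. Passing 0.20 needs removal of failures only, concentrated in arm A: three from A alone at 55 per arm (0.233), or a net excess of two from A at 61 per arm (0.206). The documents give neither the number nor the direction of violations, and the number is probably small. For major violations, rewriting the rule would also bring no clear gain. Exclusion does little harm when violations are unrelated to tolerability; keeping them as failures can then cut power to 0.647 (four in A) or raise type I error to 0.235 (four in B). Neither handling is best in every case, and 16.3 already makes a defensible choice. The conclusion assumes that analysts apply the 16.3 definition as it stands and that unknown cycle 3 status is rare.
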